11.1 Study Hypotheses

The primary objective of this study will be assessed through estimation rather than hypothesis testing, as this is a Phase I study with small sample sizes. The study includes eight subjects in each of the first three cohorts and twelve subjects in the fourth cohort.

The secondary objective of defining the multi-dose kinetics of oxfendazole will be assessed using a descriptive analysis with no formal hypothesis test. For the secondary objective of the determination of the effect of food on the kinetics of oxfendazole, equivalence between the fasting (water is permitted) and fed conditions will be tested using 90% confidence intervals and 80-125% equivalence limits for AUC_{0-∞}, AUC₀₋₂₄, and C_{max} in accordance with FDA guidance.

<http://www.fda.gov/downloads/RegulatoryInformation/Guidances/UCM126833.pdf>

11.2 Sample Size Considerations

The sample sizes were selected to obtain preliminary safety information on a small cohort of subjects before proceeding to larger trials. In this Phase 1 study, we are concerned with rates of adverse events, which theoretically could occur due to oxfendazole treatment. The dosing regimens with respective sample sizes are described in Table 4 below:

Table 4. Sample sizes for each dose regimen

Cohort	Dose Regimen	Sample size
1	3 mg/kg daily for 5 days	8
2	7.5 mg/kg daily for 5 days	8
3	15 mg/kg daily for 5 days	8
4	Single dose of 3 mg/kg after fasting (water is permitted) with cross-over to single dose of 3 mg/kg after high-fat meal.	12

The study will produce preliminary estimates of adverse event rates for each dosing regimen. The true adverse event rates within each dosing regimen are unknown. The below table displays probabilities of observing at least one adverse event within a cohort assuming different true underlying event rates and sample sizes. For example, if an adverse event has a true rate of 0.20, then the probability of observing at least one adverse event among 8 subjects is 0.83. There is a 0.93 probability of observing the event among 12 subjects. The probabilities were calculated using R statistical software, version 3.2.2.

Table 5. Probabilities of observing adverse events for various event rates and sample sizes

True Rate of Adverse Event	Probability of observing at least one adverse event within a cohort	
	Among 8 subjects	Among 12 subjects
0.01	0.08	0.11
0.05	0.34	0.46
0.08	0.49	0.63
0.10	0.57	0.72
0.15	0.73	0.86
0.20	0.83	0.93

With 12 total participants to assess the secondary objective of the determination of the effect of food on the kinetics of oxfendazole, the power is 80% when the coefficient of variation is less than 0.175 and 64% when the coefficient of variation is 0.2.

11.3 Planned Interim Analyses (if applicable)

No interim analyses are planned.

11.3.1 Safety Review

The SMC will have a formal meeting after all subjects in groups 1-3 have completed the day 10 study visit. This meeting will be scheduled expeditiously, but this SMC review is not required prior to enrollment into study group 4. This report will summarize adverse events as described in section 11.4.3 below. Additional safety review may occur if halting rules are met.

11.4 Final Analysis Plan

The final analysis will be performed and clinical study report completed when all primary and secondary endpoint data are available. This study, like other Phase 1 studies, is exploratory rather than confirmatory; its purpose is to estimate adverse event rates and characterize pharmacokinetic profiles than to test formal statistical hypotheses. Estimates will be presented with their 95% confidence intervals. Results will be presented in tabular format, as well as graphically when appropriate.

11.4.1 Populations for Analysis

Safety Population

All participants who receive study drug and for whom any safety data are available will be included in the safety population.

PK Analysis Population

All participants who receive study drug and have at least one evaluable PK concentration will be eligible for the PK analysis population.

11.4.2 Analysis of Demographics

Demographic characteristics (age, gender, race, ethnicity) of each cohort will be summarized numerically.

11.4.3 Analysis of Safety

Adverse experiences (spontaneous reports) will be coded into MedDRA® preferred terms. The number of subjects experiencing unsolicited adverse events and the number of spontaneous events, classified using MedDRA® System Organ Classes and Preferred Terms, reported throughout the study after treatment administration will be tabulated by cohort. The severity and relationship to study product of the unsolicited adverse events will also be assessed. Serious adverse events will be described. A complete listing of adverse experiences for each subject will provide details including severity, relationship to treatment, onset, duration, and outcome. Solicited clinical laboratory results and vital signs will be graded and summarized by cohort and study day.

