3 OBJECTIVES

3.1 Study Objectives

Primary:

- To assess the safety of oxfendazole administered daily for five days
- To assess the safety of oxfendazole administered as a single dose with or without food

Secondary:

- To define the multi-dose kinetics of oxfendazole
- To determine the effect of food on the kinetics of oxfendazole

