3.2 Study Outcome Measures

3.2.1 Primary endpoint:

- The rate of adverse events (AEs) related to oxfendazole within 10 days of receipt of oxfendazole given for 5 sequential, daily oral doses of either 3, 7.5 or 15 mg/kg
- The rate of adverse events (AEs) related to oxfendazole within 7 days of receipt of oxfendazole given as a single daily dose of 3 mg/kg on days 1 and 8 either following an 8 hour fast or following a high fat meal.

3.2.2 Secondary endpoints:

- Plasma C_{max}, T_{max}, AUC, T_{1/2} of oxfendazole at specified time points following each dose of a 5 day daily regimen of either 3, 7.5 or 15 mg/kg
- Plasma C_{max}, T_{max}, AUC, T_{1/2} of oxfendazole at specified time points following a single dose of oxfendazole of 3 mg/kg on days 1 and 8 administered after an 8 hour fast or after a high fat meal.

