11 STATISTICAL CONSIDERATIONS

This is an open-label Phase I study to assess the safety and pharmacokinetics of oxfendazole in healthy males and nonpregnant females, ages 18-45. The primary objectives are to assess the safety of oxfendazole administered daily for five days and to assess the safety of oxfendazole administered as a single dose with or without food. The secondary objectives are to define the multi-dose kinetics of oxfendazole and to determine the effect of food on the kinetics of oxfendazole.

Primary endpoints:

1. The rate of adverse events (AEs) related to oxfendazole within 10 days of receipt of oxfendazole given for 5 sequential, daily oral doses of either 3, 7.5 or 15 mg/kg
2. The rate of adverse events (AEs) related to oxfendazole within 7 days of receipt of oxfendazole given as a single daily dose either following an 8 hour fast or following a high fat meal.

Secondary endpoints:

1. Plasma C_{max}, T_{max}, AUC, T_{1/2} of oxfendazole at specified time points following each dose of a 5 day daily regimen of either 3, 7.5 or 15 mg/kg
2. Plasma C_{max}, T_{max}, AUC, T_{1/2} of oxfendazole at specified time points following a single dose of oxfendazole administered after an 8 hour fast or after a high fat meal.

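### The stated adverse-event tabulation (Protocol 11.4.3) pools Group 4's fasted and fed doses over the whole study, so it does not return the second primary endpoint on its natural reading

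*Protocol*

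**What the plan says.** **Objective and endpoint.** The Group 4 primary objective is "To assess the safety of oxfendazole administered as a single dose with or without food" (Protocol 3.1). The matching endpoint is the rate of AEs "related to oxfendazole within 7 days of receipt of oxfendazole given as a single daily dose", on Days 1 and 8, after a fast or a high fat meal (Protocol 3.2.1). Protocol 11 restates it with the same 7-day window, for oxfendazole "given as a single daily dose either following an 8 hour fast or following a high fat meal".

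**Tabulation.** Protocol 11.4.3 counts subjects with AEs and numbers of events, "reported throughout the study after treatment administration will be tabulated by cohort". It adds: "The severity and relationship to study product of the unsolicited adverse events will also be assessed". It also plans a per-subject listing that includes onset and relationship. Laboratory results and vital signs are summarised by cohort and study day.

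**What the cohort is.** Table 4 in Protocol 11.2 gives cohort 4 as a single regimen of 12 subjects: "Single dose of 3 mg/kg after fasting (water is permitted) with cross-over to single dose of 3 mg/kg after high-fat meal".

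**Related rules.** Protocol 11.4 promises that "Estimates will be presented with their 95% confidence intervals". Protocol 11.4.1 states: "All participants who receive study drug and for whom any safety data are available will be included in the safety population". Protocol 11.4.4 does summarise Group 4 by fasted or fed condition, but for pharmacokinetic parameters. The SAP limits itself to pharmacokinetics (SAP 1) and has no AE output.

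**The concern.** The endpoint has three parts: relatedness, a 7-day window after each dose, and the feeding condition. The stated table addresses relatedness but has neither a window nor a condition. The summary by study day does not help: the order of conditions is randomised 1:1 (Protocol 5.3.1), so each dosing day mixes fed and fasted subjects.

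If the endpoint is meant by condition, the table named in the plan cannot supply it. The 7-day endpoint covers most of the assignment of events to doses, but the plan does not settle which dose takes an event near the second dose. Nor does it state the denominator for each condition. A subject whose second dose is withheld (Protocol 5.4.1), or who is lost after the first (Protocol 5.4.2), stays in the safety population but was dosed in one condition only. In an open-label study these choices are better fixed before the data are examined.

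**Working it through.** **1. The plan's own figure.** Table 5 gives the probability of at least one AE among 12 subjects at a true rate of 0.20 as 0.93. Check: 1 − (1 − 0.20)^12 = 0.931. All 12 cells of Table 5 reproduce. The figure is per cohort and does not involve feeding condition.

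**2. What pooling hides (assumed rates).** With rates p1 fasted and p2 fed, independent within subject, the proportion of subjects with at least one event is 1 − (1 − p1)(1 − p2).
- 0.05 fasted and 0.20 fed: 1 − 0.95 × 0.80 = 0.24, or 2.88 of 12 expected.
- 0.20 fasted and 0.05 fed: 0.24 again.
- 0.128 in both: 1 − 0.872² = 0.24.

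Three different food effects on safety give the same cohort figure.

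**3. Splits that fit an observed table.** Protocol 11.4.3 tabulates both subjects and events. Suppose k of 12 subjects have one related event each, all within 7 days of a dose. Then k + 1 (fed, fasted) results fit.
- k = 1: two results, 1/0 and 0/1.
- k = 2: three results, 2/0, 1/1 and 0/2. The fed rate is then 2/12 = 16.7%, 1/12 = 8.3% or 0/12 = 0%.
- k = 0: no ambiguity.

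**4. Precision of a by-condition table.** Exact (Clopper-Pearson) 95% intervals: 0/12 gives 0 to 26.5%; 1/12 gives 0.2 to 38.5%. If one subject is withheld from the second dose, the denominators are 12 and 11, and 0/11 gives 0 to 28.5%.

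**5. Follow-up after each dose, in elapsed days.** The second dose is on Day 8 ± 1 and the final visit on Day 14 ± 2 (Protocol 7.6 and 7.7).
- Second dose to final visit: nominal 14 − 8 = 6; shortest 12 − 9 = 3; longest 16 − 7 = 9.
- First dose to second dose: nominal 8 − 1 = 7; range 7 − 1 = 6 to 9 − 1 = 8.

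Protocol 7.6 treats Day 9 as one day after the second dose. SAP Table 13 puts the last Period 2 sample at 144 hours, and 144/24 = 6 days. Both agree with the 6-day count. Protocol 4, however, says subjects are followed for 7 days after the second dose. The 3 and 9 are limits of the visit windows, not likely values.

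**The case against.** The strongest case for the plan is that cohort is its own unit of estimation. Protocol 11.2 promises AE rates for each dosing regimen, Table 4 lists the crossover as one regimen, and Table 5 works per cohort of 12. On that reading one pooled Group 4 rate is intended and the cohort table comes close to it. This stands as a possible reading. It does not supply the 7-day window, and the with-or-without-food objective points more naturally to a rate for each condition.

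It can also be said that nothing is lost. Onset and relationship are listed, dose times and sequence are recorded, and the endpoint's window assigns most events by itself because the doses are about 7 days apart. That is correct. A reader might infer that the endpoint cannot be obtained at all, but the documents do not support this: it can be rebuilt, although no such summary is stated.

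A reader might also infer that no safety analysis plan exists anywhere. The SAP supplied confines itself to pharmacokinetics, so the documents cannot show whether a separate one exists.

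Finally, few related events may occur. In the earlier single-dose study (Protocol 2.1.2) six AEs were judged related, and the gastrointestinal ones all arose at 30 or 60 mg/kg, against 3 mg/kg here. With no related events the pooling would hide nothing.

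**Conclusion.** The point holds in a limited form. The tabulation rule the plan states does not return the second primary endpoint on its natural reading: it pools the two conditions and sets no window per dose. The effect is confined to descriptive reporting. The primary objective is handled by estimation (Protocol 11.1), and the halting rules in Protocol 9.5 do not depend on this table.

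The size is two compatible splits for one subject with one related event, and three for two subjects with one each. This assumes that related events are shown separately in the cohort table, that each falls within 7 days of a dose, and that all 12 subjects receive both doses.

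Two stronger readings should be avoided.
- Counting subjects alone gives (k + 1)(k + 2)/2, that is 3 and 6 splits, because a subject could have events in both conditions. The event counts in the same table exclude those extra cases when each subject has one event.
- A reader might take the protocol to count days inclusively, so that nominal follow-up is seven days after each dose. No such convention is stated, and Protocol 7.6 and SAP Table 13 point to 6 elapsed days after the second dose. That is in tension with the 7 days in Protocol 4, and the passages must be reconciled.

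**What to change.** Keep the cohort table and add to Protocol 11.4.3 one descriptive Group 4 table of related AEs and of all AEs, by condition (fed, fasted):
- Assign each event to the most recent dose, using actual dose time and AE onset.
- Count it only if onset is within the endpoint's 7 days of that actual dose. Events outside a window stay in the cohort table and the listing.
- Use as denominator the safety-population subjects dosed in that condition.
- Compute the promised 95% intervals by the Clopper-Pearson method.
- Report the follow-up actually observed after each dose.

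If one pooled Group 4 rate is intended, say so in Protocol 3.2.1 and still apply the 7-day window to each dose. Separately, reconcile the 7 days of follow-up in Protocol 4 with the visit days in Protocol 7.6 and 7.7.

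The cost is one extra table with wide intervals and a few sentences of text. It needs no new data, visits or subjects.

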11.4.4 Pharmacokinetic Analysis

PK parameters for oxfendazole will be calculated using non-compartmental analysis. Parameters will be summarized separately by group and dose.

Maximum concentration (C_{max}), time of maximum concentration (T_{max}), and the pre-dose trough concentrations (C_{trough}) will be directly estimated from the observed concentration-time curve. Area under the curve (AUC) will be calculated using the linear up-log down trapezoidal method. λ_z will be calculated as the negative of the slope of the terminal log-linear segment of the plasma concentration-time curve. The range of data to be used for each subject and treatment will be determined by visual inspection of a semi-logarithmic plot of concentration vs. time, but will include at least three plasma concentration-time points for λ_z to be estimable. Half-life ($t_{1/2}$) will be calculated as $\ln(2)/\lambda_z$.

In Groups 1-3, $AUC_{0-\tau}$ will be calculated as AUC to the end of the 24-hour dosing interval. Oral clearance at steady state will be calculated using $AUC_{0-\tau,ss}$ after the Day 5 (expected steady state) dose as

$$CL_{ss} / F = \frac{Dose}{AUC_{0-\tau,ss}}$$

The observed accumulation ratio (AR) following multiple dosing will be estimated using the ratio of $AUC_{0-\tau}$ following multiple and single dosing. When λ_z is estimable, AR will also be estimated using λ_z calculated following multiple dosing:

$$AR = \frac{1}{1 - e^{-\lambda_z \tau}}$$

The relationship between exposure (C_{max} and AUC) and dose, i.e., dose proportionality, will be examined using ANOVA or the power model

$$P = a \times Dose^b$$

where P represents the parameter and a and b are constants. A value of b of approximately 1 indicates linear PK.

Group 4 parameters will be summarized by condition (fasting (water is permitted) or fed). In group 4, 90% confidence intervals for ratios of key exposure parameters will be estimated using appropriate analysis of variance (ANOVA) models on the log-transformed parameters. Key exposure parameters will be C_{max} , AUC to the time of the last quantifiable concentration (AUC_{0-t}), and, when λ_z is estimable, AUC extrapolated to infinity ($AUC_{0-\infty}$).

Listings of individual subject plasma concentrations, actual blood sampling times, PK parameters, and graphs of concentration vs. time will be prepared by group. Parameter estimation using noncompartmental analysis will be done using appropriate computer software, such as Phoenix WinNonlin, as determined by the sponsor.

12 SOURCE DOCUMENTS AND ACCESS TO SOURCE DATA/DOCUMENTS

The site will maintain appropriate medical and research records for this trial, in compliance with ICH E6, Section 4.9 and regulatory and institutional requirements for the protection of confidentiality of subjects. Describe who will have access to records. As part of participating in a DMID-sponsored, DMID-affiliated, or manufacturer-sponsored study, each site will permit authorized representatives of the sponsor(s), DMID, and regulatory agencies to examine (and when required by applicable law, to copy) clinical records for the purposes of quality assurance reviews, audits, and evaluation of the study safety and progress.

Source data are all information, original records of clinical findings, observations, or other activities in a clinical trial necessary for the reconstruction and evaluation of the trial. Examples of these original documents and data records include, but are not limited to, hospital records, clinical and office charts, laboratory notes, memoranda, subjects' memory aid or evaluation checklists, pharmacy dispensing records, recorded data from automated instruments, copies or transcriptions certified after verification as being accurate and complete, microfiches, photographic negatives, microfilm or magnetic media, x-rays, and subject files and records kept at the pharmacy, at the laboratories, and medico-technical departments involved in the clinical trial. It is acceptable to use CRFs as source documents. If this is the case, it should be stated in this section what data will be collected on CRFs and what data will be collected from other sources.

13 QUALITY CONTROL AND QUALITY ASSURANCE

Following a written DMID-accepted site quality management plan, the investigational site is responsible for conducting routine quality assurance and quality control activities to internally monitor study progress and protocol compliance. The PI will provide direct access to all trial-related sites, source data/documents, and reports for the purpose of monitoring and auditing by the sponsor, and inspection by local and regulatory authorities. The PI will ensure all study personnel are appropriately trained and applicable documentation is maintained on site. DMID-designated clinical monitors will verify that the clinical trial is conducted and data are generated, documented (recorded), and reported in compliance with the protocol, ICH/GCP guidelines, and the applicable regulatory requirements. Clinical monitoring reports will be submitted to DMID.

The SDCC will implement quality control procedures beginning with the data entry system and generate data quality control checks that will be run on the database. Any missing data or data anomalies will be communicated to the site(s) for clarification and resolution.

14 ETHICS/PROTECTION OF HUMAN SUBJECTS

14.1 Ethical Standard

The investigator will ensure that this study is conducted in full conformity with the principles set forth in The Belmont Report: Ethical Principles and Guidelines for the Protection of Human Subjects of Research of the US National Commission for the Protection of Human Subjects of Biomedical and Behavioral Research (April 18, 1979) and codified in 45 CFR Part 46 and/or the ICH E6; 62 Federal Regulations 25691 (1997).

14.2 Institutional Review Board

Prior to enrollment of subjects into this trial, the approved protocol and the informed consent form will be reviewed and approved by the appropriate IRB. The responsible official for the IRB will sign the IRB letter of approval of the protocol prior to the start of this trial and a copy will be provided to DMID. Notification of the IRB's composition, or the IRB's Federal Wide Assurance number, will be provided to DMID. Should amendments to the protocol be required, the amendments will be written by the investigator and approved by DMID prior to submission to the IRB.

14.3 Informed Consent Process

Informed consent is a process that is initiated prior to the individual's agreeing to participate in the study and continuing throughout the individual's study participation. Extensive discussion of risks and possible benefits of this therapy will be provided to the subjects and their families. Consent forms describing in detail the study interventions/products, study procedures, and risks are given to the subject and written documentation of informed consent is required prior to starting intervention/administering study product. Consent forms will be IRB-approved and the subject will be asked to read and review the document. Upon reviewing the document, the investigator will explain the research study to the subject and answer any questions that may arise. The subjects will sign the informed consent document prior to any procedures being done specifically for the study. The subjects should have the opportunity to discuss the study with their surrogates or think about it prior to agreeing to participate. The subjects may withdraw consent at any time throughout the course of the trial. A copy of the informed consent document will be given to the subjects for their records. The rights and welfare of the subjects will be protected by emphasizing to them that the quality of their medical care will not be adversely affected if they decline to participate in this study.

14.3.1 Informed Consent/Assent Process (in Case of a Minor)

Not applicable

14.4 Exclusion of Women, Minorities, and Children (Special Populations)

This study will be inclusive of all healthy adults who meet the inclusion/exclusion criteria, regardless of religion, sex, or ethnic background. Only individuals, who are 18 to 45 years old, inclusive, will be included at this time. Women of childbearing potential and children are excluded for safety reasons. Prisoners are excluded due to the rigorous study schedule that would not be feasible in an incarcerated population. Should the outcome of this study be deemed acceptable, additional trials may be initiated in other populations.

